9.1 Statistics and Interim Analysis

Feasibility Phase

No statistical tests will be conducted with the difficulties encountered/solutions identified at the weekly meetings of the study team. Rather, all difficulties encountered will be discussed on a weekly basis and be collated into a single table at the end of the feasibility phase. This information will be used to design the manual of operations for the larger RCT.

Recruitment rate will be presented as a rate of recruitment per week and retention rate will be presented as a proportion of recruited participants that continued to wear the device to the end of the feasibility phase.

The mean, standard deviation, median, and interquartile range will be presented for insulin to carbohydrate ratio, insulin active time, and percent time in various glycaemic ranges at the end of the phase.

No interim analyses are planned apart from the DSMB safety review reported above.

RCT Phase

Data collected at baseline and Visit 6 will be used to assess the effectiveness of AHCL therapy as compared to standard therapy.

To test for an effect of treatment group on the primary outcome, an ANCOVA including treatment, baseline percent time in range adjusting for minimisation factors will be conducted on an intention to treat basis. Multiple imputations will be used to handle missing data: a multivariate normal imputation approach will be taken. Results will be presented as the mean difference in the percent time in target range at the end of the study between treatment arms with 95% confidence interval and p value.

Model residuals will be used to assess model fit. If the residuals indicate poor model fit, the outcome variable will be transformed and the model refitted and evaluated. If poor model fit cannot be addressed, nonparametric analysis will be performed.

In the event that residuals are not normally distributed: the Mann–Whitney–Wilcoxon (Wilcoxon Rank-Sum) Test will be employed if raw data are symmetric; if raw data are non-symmetric, bootstrap methods will be used to test the difference between groups.

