Continuous secondary outcomes (glycaemic, auxological, clinical, psychosocial) will be analysed using the ANCOVA approach described above. The same assessment of model residuals will be conducted, and the appropriate analysis approach utilised. Where parametric methods are employed using the untransformed outcome measure, mean difference with 95% CI will be presented; where data are transformed, the retransformed effect with 95% confidence intervals will be presented as an indication of the relative effect of the intervention; where non-parametric methods are employed, Hodges-Lehmann median difference with robust 95% CI will be presented.

Secondary count outcomes will be analysed using Poisson regression or, where overdispersion is apparent, negative binomial model with a maximum likelihood-estimated dispersion parameter. 'Exposure' will be the number of hours wearing the sensor for CGM-derived outcomes and total number of days enrolled in the study for non-CGM-derived outcomes.

To assess the cost effectiveness of the intervention, the 'cost per quality of life year (QALY)' will be calculated using an incremental cost effectiveness ratio.

All hypothesis testing will be two-sided with an α of 0.05. No corrections for multiplicity are planned to control Type I error; rather, the effectiveness of the intervention will be assessed based on the clearly specified primary outcome; secondary outcomes are exploratory in nature and will be labelled as such in publications arising from the study.

No interim analyses are planned apart from the DSMB safety review reported above.

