9.2 Sample Size

The feasibility phase aims to recruit 12 participants. This number has been selected as it will allow sufficient participants to be enrolled to familiarise the study team with the device and identify any major difficulties that may be encountered within the protocol in the larger RCT.

The power calculation for the RCT is for a parallel study design with two groups of equal size. Based on CGM data in this age group (8, 9) we would expect control group to spend on average 55% of TIR with SD 11.5. With alpha set at 0.05, 31 participants would be required per group to have 80% power to detect an increase of 8% points. It is assumed the total dropout rate will be up to 10% based on previous studies, so we plan to recruit 70 participants in total.

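### The primary-outcome fallback in section 9.1 swaps the adjusted ANCOVA for a rank-sum test that takes no covariates, after inspecting the data and on a symmetry criterion that test does not need

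*Protocol*

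**What the plan says.** Protocol section 9.1 (RCT Phase) makes the primary analysis an intention-to-treat ANCOVA with treatment, baseline TIR and the minimisation factors, reported as a mean difference with 95% CI and p value. Section 7.2 also specifies a baseline-adjusted ANCOVA and a mean difference, and rests the claim of effectiveness on p < 0.05 in favour of the intervention. The minimisation factors (section 4.4) are age group, baseline TIR below or at least 55%, and study site.

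Two consecutive paragraphs of section 9.1 then deal with poor residuals:

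- The first transforms the outcome and refits the model. After that: "If poor model fit cannot be addressed, nonparametric analysis will be performed".
- The second takes non-normal residuals as its trigger, has no transformation step, and says that the Mann–Whitney–Wilcoxon "Test will be employed if raw data are symmetric; if raw data are non-symmetric, bootstrap methods will be used" to compare the groups.

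For continuous secondary outcomes, section 9.1 applies the same residual check and adds: "where non-parametric methods are employed, Hodges-Lehmann median difference with robust 95% CI will be presented".

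On size, section 9.2 states: "The power calculation for the RCT is for a parallel study design with two groups of equal size"; "we would expect control group to spend on average 55% of TIR with SD 11.5"; and "31 participants would be required per group to have 80% power to detect an increase of 8% points". It mentions no correlation with baseline.

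**The concern.** The rank-sum test has no place for covariates. On that branch baseline TIR, age group and site all leave the primary test, although baseline TIR is usually the strongest predictor of final TIR and all three were used to allocate participants. What is tested also changes, from a difference in adjusted means to a difference in the ranking of raw values, whereas sections 7.2 and 9.1 promise the former.

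The branch is chosen after inspecting first the residuals and then the shape of the raw data, and no criterion is given for either. Section 9.1 justifies the absence of multiplicity correction by pointing to one clearly specified primary outcome. That argument is weaker if the test of that outcome can become a transformed ANCOVA, a rank-sum test or a bootstrap.

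Raw-data symmetry is also the wrong gate. The rank-sum test does not require it, and symmetry of raw values says little about the residuals of an adjusted model.

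At stake is whether the primary p value and effect estimate answer the stated question with the precision the ANCOVA would give.

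**Working it through.** **1. Reproduce the stated sample size.** Inputs from section 9.2: difference 8 points, SD 11.5, 80% power, two equal groups. From section 9.1: "All hypothesis testing will be two-sided with an α of 0.05".

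n per group = 2 × [SD × (z₀.₉₇₅ + z₀.₈₀) / difference]² = 2 × [11.5 × (1.960 + 0.842) / 8]² = 32.4, so 33. The exact t-test needs 34.

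Power at 31 per group: 8 / (11.5 × √(2/31)) = 2.739; 2.739 − 1.960 = 0.779; Φ(0.779) = 78.2%. The t-test gives 76.9%.

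Dropout: 31 / 0.9 = 34.4, so 35 per group and 70 in total, as stated.

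The stated 31 is therefore reproduced to within rounding (a little low) as an **unadjusted** two-sample calculation. No baseline correlation enters it.

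**2. What adjustment adds.** With baseline correlation r, the SD becomes 11.5 × √(1 − r²). The protocol does not give r, so a range is shown. At 31 per group, by the same normal approximation:

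| r | Residual SD | ANCOVA power |
|---|---|---|
| 0 | 11.5 | 78% |
| 0.3 | 10.97 | 82% |
| 0.5 | 9.96 | 88% |
| 0.7 | 8.21 | 97% |

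The gain above about 78% is what a covariate-free test can forgo.

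**3. The branch that leads to rank-sum.** Under the plan, rank-sum follows only when residuals are non-normal and raw data symmetric. Symmetric heavy-tailed errors are the natural example. Simulated power at 31 per arm, SD 11.5, effect 8 (2,000–3,000 trials per setting), ANCOVA v unadjusted rank-sum:

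| Errors | r = 0.3 | r = 0.5 | r = 0.7 |
|---|---|---|---|
| t, 3 df | 83% v 92% | 89% v 87% | 95% v 83% |
| t, 4 df | not run | 87% v 82% | 95% v 79% |
| t, 5 df | not run | 87% v 81% | 96% v 77% |
| Laplace | 80% v 85% | 87% v 82% | 95% v 78% |

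A separate set of runs on the same branch gave 80–82% v 82–90% at r = 0.3, 86–90% v 79–89% at 0.5, and 95% v 76–82% at 0.7. Monte Carlo error is about 1 point (√(0.8 × 0.2 / 2,000) = 0.009), so the sets agree to within a point or two. ANCOVA type I error was about 4–6%, so tails of this kind give no validity reason to abandon it.

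**4. The two paragraphs side by side.**

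| | First paragraph | Second paragraph |
|---|---|---|
| Trigger | Residuals show poor fit | Residuals not normal |
| Next step | Transform and refit, covariates kept | Rank-sum or bootstrap |
| Nonparametric analysis | Only if poor fit remains | At once |

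Non-normal residuals are one form of poor fit, so the same finding meets both triggers and leads to different next steps.

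**The case against.** **The power target is not breached.** A reader might infer that losing the baseline adjustment takes the trial below its stated 80%. The document does not support that, because the 80% never relied on adjustment. The unadjusted comparison at 31 per arm has 77–78% by the plan's own inputs, and that small shortfall comes from the sample size. With all 70 recruits analysed (35 per arm), the unadjusted t-test has 82%.

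**Rank-sum is sometimes the better test.** With heavy tails and a correlation of 0.3 or less it equals or beats ANCOVA. This stands, and it rules out saying that the switch has no benefit.

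**The bootstrap may be adjusted.** A reader might take both fallbacks to be unadjusted. Only the rank-sum test necessarily is. Section 9.1 does not say what is bootstrapped, and a bootstrap of the ANCOVA coefficient would fit the text. Clearly skewed data go to that branch, so comparing ANCOVA with rank-sum under skew says little about this plan.

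**The switch may be rare.** If the first paragraph governs, transformation comes first and keeps the covariates. The protocol names no normality test, so no trigger rate can be given. This limits how often the problem arises, but the second paragraph as written skips that step.

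**The Hodges–Lehmann estimate** is stated for continuous secondary outcomes. For the primary outcome the protocol promises only a mean difference, so a switch to a median difference there is not documented. The rank-sum branch simply leaves the promised estimate without a matching test.

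**Conclusion.** The fallback is badly fixed and should be changed. On the rank-sum branch the primary test loses baseline TIR and the minimisation factors and no longer matches the estimate in sections 7.2 and 9.1. It is reached by inspecting the data on a criterion the test does not need, and by a route that conflicts with the paragraph before it.

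The cost is precision relative to the planned ANCOVA. At 31 per arm with symmetric heavy-tailed errors it is roughly 13–19 points of power at correlation 0.7 (95 − 82 to 95 − 76). It is smaller at 0.5, and absent or reversed at 0.3. These figures rest on an assumed correlation, assumed error shapes, and the protocol's SD and effect.

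The structural points (no covariates, the symmetry gate, two routes) need none of those assumptions. The finding does not extend to a breach of the stated 80% or to the bootstrap being unadjusted.

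**What to change.** In section 9.1:

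- Keep the ANCOVA coefficient for treatment, with baseline TIR and the minimisation factors, as the primary estimate whatever the residuals look like.
- If residuals are non-normal or heteroscedastic, take the confidence interval and p value for that same coefficient from HC3 standard errors or a bootstrap, naming one of the two in advance. State that the bootstrap already mentioned is of this adjusted coefficient.
- Delete the raw-data symmetry criterion and merge the two paragraphs into one ordered rule.
- Move the rank-sum test and Hodges–Lehmann estimate to sensitivity analysis.
- Apply the same rule to the continuous secondary outcomes.

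A single coefficient also pools in the usual way over the multiple imputations planned in sections 9.1 and 9.7.

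The cost is wording in the protocol, and in the SAP if one exists, with no change to data collection or sample size. The downside is somewhat less power than rank-sum if tails are heavy and the baseline correlation is low: at 0.3, 80–82% against 82–90%.

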9.2 Sample Size

The feasibility phase aims to recruit 12 participants. This number has been selected as it will allow sufficient participants to be enrolled to familiarise the study team with the device and identify any major difficulties that may be encountered within the protocol in the larger RCT.

The power calculation for the RCT is for a parallel study design with two groups of equal size. Based on CGM data in this age group (8, 9) we would expect control group to spend on average 55% of TIR with SD 11.5. With alpha set at 0.05, 31 participants would be required per group to have 80% power to detect an increase of 8% points. It is assumed the total dropout rate will be up to 10% based on previous studies, so we plan to recruit 70 participants in total.

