9.3 Study Power and Significance

All hypothesis testing will be two-sided with an α of 0.05.

9.4 Statistical plan deviations:

Any deviations to the original statistical plan will be reported to relevant ethics committees, governance committees and the DSMB.

9.5 Selection of participants for analyses:

The selection of participants to be included in the analyses (e.g. all randomised participants, all dosed participants, all eligible participants, or all evaluable participants).

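### Section 9.2: 31 per group does not give 80% power on the printed inputs; an unadjusted comparison gives about 77 to 78%, a small discrepancy in a stated figure

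*Protocol*

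**What the plan says.** Section 9.2 sets out the calculation: "The power calculation for the RCT is for a parallel study design with two groups of equal size". For the control arm, "we would expect control group to spend on average 55% of TIR with SD 11.5". The conclusion, at an alpha of 0.05, is "31 participants would be required per group to have 80% power to detect an increase of 8% points". Recruitment follows from that: "It is assumed the total dropout rate will be up to 10% based on previous studies, so we plan to recruit 70 participants in total".

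Section 9.2 does not give the sidedness of the test. Section 9.3 does: "All hypothesis testing will be two-sided with an α of 0.05". Section 9.1 says the same.

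Section 9.2 names no formula or test and gives no correlation between baseline and follow-up. Sections 7.2 and 9.1 fix the primary analysis as an ANCOVA on baseline time in range, and 9.1 adds the minimisation factors.

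**The concern.** Every input to a standard two-group calculation is printed, so a reader can repeat it, and the result is not 31. The number per group is slightly too small for the stated power or, equally, the stated power is slightly too high for the number.

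What is at stake is whether the sample-size statement for the primary outcome can be checked. Ethics committees and later readers will take 80% power for 8 points as a property of the design. As printed, it depends on something that 9.2 leaves out: baseline adjustment, a different SD or an effect that was rounded.

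**Working it through.** **Inputs.** Difference 8 points, SD 11.5 taken as common to both groups, alpha 0.05, power 80%, equal groups (all section 9.2); two-sided test (sections 9.1 and 9.3).

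**Step 1: the number needed, unadjusted.**
- Normal approximation: n = 2 × (1.960 + 0.842)² × (11.5/8)² = 32.4, so 33 per group.
- Two-sample t test (noncentral t): 33.4, so 34 per group.
- A one-sided test gives 26 (normal) or 27 (t; 26.3 before rounding), so a change of sidedness does not explain 31 either.

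**Step 2: power at the stated 31 per group.**
- Normal: the standard error is 11.5 × √(2/31) = 2.921. Then 8/2.921 = 2.739, and 2.739 − 1.960 = 0.779, which gives power 78.2%.
- t test: 76.9%.
- At 33 per group the values are 80.7% (normal) and 79.5% (t). At 34 the t test gives 80.7%.

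**Step 3: the difference detectable with 80% power at 31 per group.**
- Normal: 2.802 × 2.921 = 8.18 points.
- t test: 8.32 points.

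**Step 4: what would make 31 correct without adjustment.**
- With the difference held at 8, 80% power at 31 needs an SD of 11.24 (normal) or 11.06 (t).
- With the SD held at 11.5, a difference of 8.2 gives n = 30.9 (normal), and 8.3 gives 31.1 (t).

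**Step 5: dropout.**
- 62/0.9 = 68.9, so 69; the planned 70 is consistent with 31 per group.
- At the full 10% loss, 70 × 0.9 = 63 remain, or 31.5 per group. Unadjusted power is then 78.8% (normal) or 77.6% (t).
- With no loss, 35 per group give 82.9% (normal) or 81.8% (t).

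**Step 6: the planned ANCOVA.** The residual SD is 11.5 × √(1 − r²), where r is the baseline to follow-up correlation of time in range. The protocol gives no r, so the values below are assumptions. Power at 31 per group, on the t test:

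| r | Power |
|---|---|
| 0 | 76.9% |
| 0.1 | 77.3% |
| 0.2 | 78.5% |
| 0.25 | 79.5% |
| 0.3 | 80.6% |
| 0.4 | 83.6% |
| 0.5 | 87.5% |

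The 80% line is crossed at r = 0.275 with baseline as the only covariate. It is crossed at 0.280 with six covariates: baseline time in range, its two-level category, the two-level age group, and three terms for four sites. As a check, r = 0.28 gives a residual SD of 11.5 × 0.96 = 11.04, just under the 11.06 from step 4.

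**The case against.** The strongest reply is that the gap is trivial and the benchmark is not the planned analysis. By the normal approximation the shortfall is 2 per group and 1.8 points of power. Section 9.2 prints the effect as a whole number, and a value of 8.2 or 8.3 that was rounded would account for 31. The primary analysis adjusts for baseline time in range, measured by CGM in the same child about three months earlier, and a correlation of only about 0.28 is enough. Dropout is a ceiling, and the analysis is by intention to treat with multiple imputation. Unadjusted power for the 70 recruited therefore lies somewhere between the 63-evaluable and full-data figures.

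Most of this stands, and it limits the point. A reader might infer that the trial is underpowered, or that the design lacks 80% power. The documents do not support that: it would be true of the planned ANCOVA with 31 per group only if the correlation were below about 0.28, and nothing in the protocol suggests so. A reader might also infer that the SD is a misprint for 11.0, since the t test then needs 30.7, so 31. That is a guess, because a slightly different SD or an unrounded effect explains 31 as well.

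The reply does not make 31 follow from the printed inputs. Neither unadjusted two-sided formula returns it, and a correlation that is not stated cannot support a stated number. Section 9.1 also allows a rank-sum or bootstrap comparison of the groups if the model fits poorly, and the gain from the covariate may not carry over to that.

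**Conclusion.** The point holds as a minor discrepancy. On the inputs printed in 9.2, with the two-sided test of 9.3, an unadjusted comparison needs 33 to 34 per group against the stated 31. Power at 31 falls short of the claim by about 2 to 3 percentage points. These figures assume a common SD of 11.5 and a difference of exactly 8 points.

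The adequacy of the trial is a separate question, and the protocol gives no ground to doubt it. Whether the planned analysis has 80% power turns on a correlation that the protocol does not state.

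**What to change.** Restate the sentence in 9.2, without enrolling more children, in one of two ways:

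- *With 31 evaluable participants per group, power to detect 8 points is about 77 to 78% for an unadjusted comparison (SD 11.5, two-sided alpha 0.05).*
- *The planned ANCOVA gives at least 80% power to detect 8 points with 31 per group, assuming a baseline to follow-up correlation of time in range of at least 0.28.* The sponsor should give the basis for that correlation.

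If the 31 came from a different SD or an unrounded effect, print that figure instead and name the formula used.

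The cost is one sentence. Recruitment, schedule and analysis do not change. Under the first option the stated power becomes slightly less favourable.

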9.3 Study Power and Significance

All hypothesis testing will be two-sided with an α of 0.05.

9.4 Statistical plan deviations:

Any deviations to the original statistical plan will be reported to relevant ethics committees, governance committees and the DSMB.

9.5 Selection of participants for analyses:

The selection of participants to be included in the analyses (e.g. all randomised participants, all dosed participants, all eligible participants, or all evaluable participants).

9.6 Data management

Data collected from each site will be stored in the respective study sites' secured servers, in accordance to data storage policies in each site. These data will all be entered, in a de-identified manner into a robust

data capture platform, REDCap, in which the forms were built and validated by a data manager based in Telethon Kids Institute.

All anonymised data will not be able to be linked back to any individual participant. Data will be stored on secure servers and electronic device capture systems with secure access for study staff only. All data will be stored at least for 25 years in line with GCP requirements on secure servers. Hard copies of participant notes will be stored in secure filing cabinets at each site and archived in secure facilities' at the end of the study.

All anonymised data will be risk rated at the completion of the study and stored in data repositories according to the Institution's data sharing policies and plan, and may be used for unspecified future research. Only published and permanently de-identified data will be deposited into publicly accessible repositories which will be safeguarded by Australian Data Archives (ADA) through a data sharing agreement with Telethon Kids Institute. The ADA main server is based in ANU and is a Core Trust Seal Certified repository.

Medtronic CareLink® System:

This system allows the study device to send information over the internet using a telecommunication network (such as a cellular network, wireless network, etc.). The information available from the Medtronic CareLink system is the same information the study team would collect from your device during an in-person office visit. Medtronic will receive participant's coded (deidentified) device data from CareLink®.

Medtronic takes steps to protect the privacy of the health information sent to the Medtronic CareLink Network over the internet. However, Medtronic cannot guarantee the health information is protected against unauthorised interception.

9.7 Procedures for missing, unused and spurious data:

Multiple imputations using multivariate normal regression imputation will be employed to account for missing/spurious data. Analysis using complete case and multiple imputation methods will be presented.

10 Monitoring / Audit

